3.1 Subjects

Healthy adult subjects

3.2 Inclusion Criteria

Subjects who meet all of the following criteria and who have the capability of giving informed consent will be included in the study.

- (1) Healthy adult male or female volunteers
- (2) Japanese
- (3) Subjects aged between 20 and 45 years at the time of informed consent
- (4) Subjects who have thoroughly understood the contents of the study and voluntarily provided written informed consent to participate in the study

[Rationales for setting]

- (1), (2), (3) Age-restricted healthy adult volunteers were selected as the study population in order for the subject backgrounds to be uniform as much as possible and for this study to conform with the "Guideline for Bioequivalence Studies of Generic Products" (PFSB/ELD Notification No. 0229-10 dated February 29, 2012) [1] and the Guidance for Industry: Bioavailability and Bioequivalence Studies Submitted in NDAs or INDs General Considerations (March 2014) [2], which specify that the subjects should be healthy adult volunteers in principle. In addition, the subjects were limited to Japanese in order for PK to be evaluated in Japanese.
- (4) To observe the provisions for subject protection in the Guidelines for Good Clinical Practice (GCP).

3.3 Exclusion Criteria

Subjects who meet any of the following criteria between screening and investigational product administration will be excluded from the study.

- (1) Subjects with a current or previous history of cardiac, hepatic, renal, gastrointestinal, respiratory, psychiatric/nervous, hematopoietic, or endocrine diseases, and those whom the investigator (or subinvestigator) deems unsuitable for the study
- (2) History of drug or food allergies
- (3) History of alcohol or drug abuse or dependence
- (4) Body mass index (BMI) of <18.0 or >30.0, or a body weight of <50 kg (BMI formula: body weight [kg]/height [m]², rounded to one decimal place)
- (5) Positive test for any of the following at screening: Hepatitis B surface antigen, serological test for syphilis, hepatitis C virus antibody, or human immunodeficiency virus antigen/antibody
- (6) Any clinically significant 12-lead ECG abnormality or QTcF interval ≥450 msec
- (7) Blood donation or sampling with a total volume of ≥400 mL within 12 weeks, ≥200 mL within 4 weeks, or ≥800 mL within one year before providing informed consent
- (8) Blood component donation or blood sampling within 2 weeks before providing informed consent

CONFIDENTIAL

- (9) Subjects who have undergone any surgery known to affect the gastrointestinal absorption of drugs (except for appendectomy and herniotomy)
- (10) Female subjects who do not agree to use an effective method of contraception from screening or 2 weeks before the start of investigational product administration, whichever comes earlier, to 14 days after the completion (or discontinuation) of investigational product administration. Male subjects who do not agree to use an effective method of contraception from the start of investigational product administration to 14 days after the completion (or discontinuation) of investigational product administration
- (11) Subjects who have previously received edaravone
- (12) Subjects who have participated in another clinical study and received a investigational product within 12 weeks before providing informed consent
- (13) Subjects who have used any drugs other than the single use of acetylsalicylic acid within 7 days before the initiation of investigational product administration
- (14) Use of alcohol or any products containing xanthin or caffeine within 24 hours before screening and visit on Day -1
- (15) Use of any nutritional supplement(s) within 7 days before the initiation of investigational product administration
- (16) Use of grapefruit, grapefruit juice, or any processed food(s) containing these substances within 24 hours before screening and visit on Day -1
- (17) Use of any tobacco or nicotine-containing product(s) within 24 hours before screening and visit on Day -1
- (18) Female subjects who have a positive pregnancy test at screening and on Day -1, are pregnant or breast feeding, or plan to get pregnant during the study.
- (19) Subjects judged by the investigator (or subinvestigator) to be unsuitable for the study for any other reason

Note) Periods are defined as follows:

- One year before informed consent is the same day of the preceding year.
- Twelve (2) weeks before informed consent is the same day of the preceding week 12 (2).
- Seven days before start of dosing is the same day of the preceding

[Rationales for setting]

- (1) To ensure the safety of subjects and to exclude unhealthy subjects.
- (2), (3), (5), (6), (19) To perform the study safely and ethically.
- (4) To reduce PK variability due to BMI differences.
- (7), (8) To ensure the safety of subjects, volumes and intervals of blood sampling were set with reference to the "Enforcement Regulations for the Act on Securing a Stable Supply of Safe Blood Products."
- (9), (13), (15), (16), (17) To avoid a possible effect on PK.
- (10), (18) To assure subject safety, even though there were no toxicity findings at the highest dose of 200 mg/kg in the reproductive and developmental toxicity studies.
- (11), (14) To avoid possible effects on assessment results of this study.

CONFIDENTIAL

(12) To perform the study ethically and to avoid any unpredictable effects of drugs whose efficacy and safety have not been established.

CONFIDENTIAL

4. Explanation and Informed Consent

4.1 Preparation of Written Information and Informed Consent Form

The investigator will prepare written information and the informed consent form. The informed consent form and written information will consist of either a unified document or a set of documents. The document will be revised as necessary.

The prepared and revised documents shall be submitted to the sponsor and approved by the institutional review board (IRB) prior to initiation of the study.

4.2 Contents of the Written Information

The written information for subjects should include explanations regarding the following:

- (1) That the study involves research.
- (2) Study Objectives
- (3) The name, title, and contact information of the investigator or subinvestigator.
- (4) Study methods (including aspects of the study that are experimental, inclusion criteria, and the probability for random allocation to each treatment).
- (5) That there is no intended benefit of the investigational product on the subject's mental and physical health, and foreseeable inconvenience to the subject.
- (6) The expected duration of the subject's participation in the study.
- (7) That the subject's participation in the study is voluntary and that the subject may refuse to participate or withdraw from the study at any time, without penalty or loss of benefits to which the subject is otherwise entitled.
- (8) That the monitor(s), auditor(s), IRB, and regulatory authority(ies) will be granted direct access to the subject's original medical records and data, without violating the confidentiality of the subject, to the extent permitted by applicable laws and regulations and that, by signing a written informed consent form, the subject is authorizing such access.
- (9) If the results of the study are published, the subject's identity will remain confidential.
- (10) The person(s) to contact for further information regarding the study and the rights of study subjects, and whom to contact in the event of a study-related injury.
- (11) The compensation and treatment available to the subject in the event of a study-related injury.
- (12) The type of IRB that reviews and discusses the appropriateness of the concerned study, the matters to be reviewed and discussed at the IRB, and other study-related issues for the IRB.
- (13) The approximate number of subjects involved in the study.
- (14) That the subject will be informed in a timely manner if information becomes available that may be relevant to the subject's willingness to continue participation in the study.
- (15) The foreseeable circumstances and reasons under which the subject's participation in the study may be terminated.
- (16) The anticipated expenses, if any, to the subject for participating in the study.
- (17) The anticipated prorated payment, if any, to the subject for participating in the study (including the calculation method of the payment).
- (18) The subject's responsibilities.

CONFIDENTIAL

4.3 Methods of Obtaining Informed Consent

- (1) Prior to the start of the study, the investigator (or subinvestigator) will provide each prospective subject with an informed consent form and written information approved by the IRB, as well as a thorough explanation regarding the study. Study collaborators can also give supplementary explanations to prospective subjects. The explanation provided to the prospective subjects should be expressed in plain words and expressions whenever possible so that he/she can easily understand the information. Each prospective subject must be given ample opportunity to inquire about the details of the study and receive answers to his/her satisfaction. The investigator (or subinvestigator) will obtain written consent to participate in the study from each prospective subject at his/her free will, after acquiring a thorough understanding.
- (2) On the informed consent form, the investigator (or subinvestigator) who has provided an explanation and the prospective subject should sign or affix their name and seal with the date of entry. If a study collaborator has provided a supplementary explanation, he/she should also sign or affix his/her name and seal to the form with the date of entry.
- (3) Prior to each subject's participation in the study (screening), the investigator (or subinvestigator) will issue a copy of the signed or named and sealed informed consent form with the date of entry, together with written information to the subject and retain the original, in accordance with the rules at the study site.
- (4) The investigator (or subinvestigator) will record the date of consent and the version of the informed consent form and written information used for explanation in each subject's case report form (CRF).

4.4 Revision of the Informed Consent Form and Written Information

- (1) When any new and important information is obtained that may affect the consent of the subjects, the investigator (or subinvestigator) shall immediately provide the subjects with such information orally, confirm the intention of the subjects to continue participation in the study, and record the results in the medical records.
- (2) Based on the information, the investigator will promptly judge whether it is necessary to revise the informed consent form and written information.
- (3) When the investigator judges it necessary to revise the informed consent form and written information, he/she shall immediately perform these revisions and obtain approval from the IRB.
- (4) The investigator (or subinvestigator) will inform the subjects undergoing the study of such information using the informed consent form and written information that has been newly-approved by the IRB, and obtain a freely given written consent from each subject to continue participation in the study.
- (5) In the same manner as the first consent, the investigator (or subinvestigator) who has provided an explanation and the subject will sign or affix their name and seal with the date of entry. If a study collaborator has provided a supplementary explanation, he/she should sign or affix his/her name and seal to the form with the date of entry.
- (6) The investigator (or subinvestigator) will issue a copy of the signed or named and sealed informed consent form with the date of entry, together with written

CONFIDENTIAL

information to the subject and retain the original, in accordance with the rules at the study site.

(7) The investigator (or subinvestigator) will record the date of consent and the version of the informed consent form and written information used for explanation in the CRF.

CONFIDENTIAL

5. Study Design

5.1 Phase and Type of the Study

Phase of the study

: Phase I

Type of the study

: Clinical pharmacology study

5.2 Study Design

5.2.1 Type and Details of Cohorts

Single-dose, randomization, open-label, crossover study

| Subjects | Period I | Period II |
|---|---|---|
| Advance administration of Edaravone oral suspension group (21 subjects) | Edaravone oral suspension 105 mg | Edaravone intravenous formulation 60 mg |
| Advance administration of Edaravone intravenous formulation group (21 subjects) | Edaravone intravenous formulation 60 mg | Edaravone oral suspension 105 mg |

Forty-two subjects are randomly allocated to two groups of 21 subjects. It is carried out by the two-period, two-sequence crossover, randomization, open-label study. The duration of hospitalization will be 7 days and 6 nights.

| | | | | Period I | Period II | \neg | | |
|----------------------------|---------------|-----------|--------|----------|----------------------------|-----------|-----|----------------------------|
| Day | y -3 0 | Day -1 | Day 1 | Day | 4 | Day 6 | 5 1 | Day 11 |
| Obtaining informed consent | Screening | Admission | † ‡ | | daravone PO daravone IV | Discharge | - | End-of-study assessment |

5.2.2 Study Period and Evaluation Period

Study period: The study period is defined as the period from the time of obtaining the informed consent to the time of completion of the end-of-study assessment or discontinuation assessment (for subjects who have entered into the follow-up period, to the time of completion or termination of the follow-up).

Screening: Subjects providing informed consent will be screened for eligibility to select subjects meeting all of the inclusion criteria and none of the exclusion criteria (42 subjects with a few reserve subjects).

Evaluation period: The evaluation period is defined as the period from completion of dosing of the investigational product in Period 1 to completion of the end-of-study assessment or discontinuation assessment.

End-of-study assessment: The prespecified observations and tests will be performed as the end-of-study assessment, 7 days (±2 days) after the last dose of the investigational product.

CONFIDENTIAL

[Rationales for setting]

A crossover design was selected for this study in order for PK parameters to be precisely compared in a small number of subjects in accordance with the "Guideline for Bioequivalence Studies of Generic Products" (PFSB/ELD Notification No. 0229-10 dated February 29, 2012) [1] and the Guidance for Industry: Bioavailability and Bioequivalence Studies Submitted in NDAs or INDs - General Considerations (March 2014) [2].

5.3 Methods of Blinding and Randomization

5.3.1 Blinding Methods

This study will be conducted as an open-label study.

5.3.2 Methods of Randomization and Allocation

The person in charge of subject assignment will create a randomization key code table according to the prespecified subject assignment procedures and provide it to the investigator. The investigator (or subinvestigator) will assign a screening number to all subjects, from which they will identify actual and reserve subjects (For reserve subjects, the order of enrollment will be determined in advance.). A subject ID code will be randomly assigned to the screening number of each subject. Then, subjects will be allocated to one of 2 groups in the ascending order of subject ID code. If subjects drop out after allocation and before drug administration, they will be replaced with reserve subjects in reserve subject inclusion order. The Investigator (or subinvestigator) or study collaborator will submit a copy of the randomization key code table to the sponsor. Details of randomization will be specified in documented subject assignment procedures.

5.4 Endpoints

5.4.1 Safety Assessments

- (1) Adverse events and adverse drug reactions
- (2) 12-lead ECG
- (3) Laboratory tests
- (4) Vital signs

5.4.2 Pharmacokinetic Assessments

- (1) Drug concentration (in plasma and urine)
 Unchanged edaravone, sulfate conjugate, and glucuronide conjugate
- (2) Pharmacokinetic parameters

Confirmatory PK parameters:

Unchanged edaravone: AUC_{0-t} , $AUC_{0-\infty}$, and C_{max} (t: Final concentration measurable time point)

CONFIDENTIAL

Reference PK parameters:

Unchanged edaravone (after intravenous administration): AUC₀₋₂₄, AUC_{0-t}, AUC_{0-∞}, t_{max} , $t_{1/2}$, Kel, MRT, CL, V_z , V_{ss} , Ae, Ae%, CLr Unchanged edaravone (after oral administration): AUC₀₋₂₄, AUC_{0-t}, AUC_{0-∞}, t_{max} , $t_{1/2}$, Kel, MRT, CL/F, V_z /F, V_{ss} /F, Ae, Ae%, CLr/F, F Sulfate conjugate and glucuronide conjugate: AUC_{0-t}, AUC₀₋₂₄, AUC_{0-∞}, C_{max} , t_{max} , $t_{1/2}$, Kel, Ae, Ae%

[Rationales for setting]

Parameters required for PK evaluation were selected with reference to the "Guideline for Bioequivalence Studies of Generic Products" (PFSB/ELD Notification No. 0229-10 dated February 29, 2012) [1] and the Guidance for Industry: Bioavailability and Bioequivalence Studies Submitted in NDAs or INDs - General Considerations (March 2014) [2], and "Clinical Pharmacokinetic Studies of Pharmaceuticals" (PFSB/ELD Notification No. 796 dated June 1, 2001) [3].

CONFIDENTIAL

6. Sample Size and Planned Study Period

6.1 Sample Size

Total of 42 subjects

[Rationales for setting]

The necessary total number of subjects was calculated using the data on $AUC_{0-\infty}$ and C_{max} of unchanged drug obtained in the previous studies (protocol No.: MT-1186-J01, MT-1186-J02, and MCI-186-J25). The calculation was performed so that for $AUC_{0-\infty}$, the two-sided 90% confidence interval (CI) of the mean ratio of edaravone oral suspension 105 mg to edaravone intravenous formulation 60 mg would fall within the bioequivalence criterion of 0.8 to 1.25, and for C_{max} , the lower limit of the two-sided 90% CI would exceed 0.8.

The SDs of AUC_{0-∞} and C_{max} were assumed to be 0.232 and 0.706, respectively, on the basis of the results of MT-1186-J02 study. The AUC_{0-∞} and C_{max} of edaravone oral suspension 105 mg were estimated to be 1828 ng·hr/mL and 1661 ng/mL, respectively, by using the Sigmoid Emax Model on the basis of the results of MT-1186-J01 and MT-1186-J02 studies. The AUC_{0-∞} and C_{max} of edaravone intravenous formulation 60 mg were estimated to be 1738 ng·hr/mL and 1195 ng/mL, respectively, on the basis of the results of MCI-186-J25 study. Thus, assuming that the ratios of the population means of AUC_{0-∞} and C_{max} of edaravone oral suspension 105 mg to edaravone intravenous formulation 60 mg are 1.06 and 1.40 (round up), respectively, the necessary total numbers of subjects calculated on the basis of 2 one-sided tests (significance level 5%, power \geq 90%) were 36 and 24, respectively. Accordingly, the total number of subjects was set at 42 in consideration of 36 subjects with 6 subjects expected to drop out.

In consideration of the above results and dropouts, the total number of subjects was set at 42 (21 per group).

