13.4.2 Pharmacokinetics

Regarding comparison between pharmacokinetics of edaravone oral suspension and those of edaravone intravenous formulation, the confirmatory PK parameters, $AUC_{0-\infty}$, AUC_{0-t} , and C_{max} , will be log-transformed, and if the 90% confidence interval of the mean log-transformed values obtained from the analysis of variance with administration of edaravone oral suspension or edaravone intravenous formulation, subjects, study periods, and concequences as factors fall within the range of log (0.80) to log (1.25), pharmacokinetics of edaravone oral suspension and edaravone intravenous formulation will be judged equivalent.

Separately from the judgement, mean values, geometric mean values, geometric mean value ratios, and 90% CI of $AUC_{0-\infty}$, AUC_{0-t} , and C_{max} will be presented for comparison. In addition, other reference PK parameters except for t_{max} will be log-transformed in principle, and the same analysis as the above will be performed for evaluation reference.

For plasma concentrations of unchanged edaravone, sulfate conjugate, and glucuronate conjugate after administration of edaravone oral suspension or edaravone intravenous formulation, summary statistics (number of subjects, mean values, standard deviations, median, minimum, and maximum values, etc.) at each blood sampling will be presented.

Summary statistics (number of subjects, mean values, standard deviations, median, minimum, and maximum values, geometric mean values, and their 95% confidence intervals) of plasma and urine pharmacokinetic parameters of unchanged edaravone, sulfate conjugate, and glucuronate conjugate after administration of edaravone oral suspension or edaravone intravenous formulation will be presented.

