13.5 Changes in the Statistical Analysis Plan

If the statistical analysis plan in this section is changed prior to data lock, both the details of the change and reason will be specified in the Statistical Analysis Plan and Clinical Study Report. If any analytical method is changed or added after data lock, details of the change and reason will be specified in the revised Statistical Analysis Plan and Clinical Study Report, and the results will be divided into those before and after the change or addition.

14. Protocol Compliance, Deviations, and Changes

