### 6.3. Data Review Meeting

Prior to database lock, a data review meeting (DRM) was conducted at 3 September 2019. Protocol deviations, protocol defined analysis populations was confirmed during the meeting.

As results of data review, no subject was excluded from safety analysis and PK analysis. Although some deviations were confirmed, it was judged that there were no impact on the safety evaluation and PK evaluation, and was included in the safety analysis and PK analysis.

The PK data handling was assessed during DRM. All PK data were considered valid, except concentration data at one PK sampling out from the allowable time window, which were included in the calculation of PK parameters but not included in the summary tables or figures for plasma concentrations.

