### **8.4.2. Analysis of Primary Endpoints**

The parameters  $AUC_{0-t}$ ,  $AUC_{0-\infty}$  and  $C_{max}$  of unchanged edaravone will be log transformed prior to statistical analysis. The analysis will be by analysis of variance (ANOVA) taking account of formulation (oral suspension or intravenous formulation). Factors accounting for the following sources of variation: sequence, subjects nested in sequences, period, and treatment. Estimates of mean difference between formulations (oral suspension minus intravenous formulation) on the log scale and 90% CI for the difference (based on the residual mean square in the ANOVA) will be back transformed to present means and 90% CI for the ratio of oral suspension to intravenous formulation.

90% CI for the ratio of  $AUC_{0-t}$ ,  $AUC_{0-\infty}$  and  $C_{max}$  of unchanged edaravone which lie entirely within the limits of 0.8000 to 1.2500 provides bioequivalence between intravenous formulation and oral suspension. As reference, the same analysis will also be on  $AUC_{0-t}$ ,  $AUC_{0-\infty}$  and  $C_{max}$  of sulfate conjugate and glucuronide conjugate and other reference pharmacokinetic parameters of unchanged edaravone, sulfate conjugate, and glucuronide conjugate, such as  $t_{max}$ ,  $AUC_{0-all}$ ,  $MRT_{0-\infty}$ , and  $Kel$ .  $T_{max}$  will not be log transformed prior to statistical analysis.

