## 10. CHANGE FROM THE PROTOCOL

There are currently no changes to analysis from protocol.

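### The 90% power stated for Cmax belongs to a lower-limit-only test; under the planned two-sided rule, at the planned ratio of 1.40, power for Cmax and for the overall conclusion is below 1%

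*Protocol*

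**What the plan says.** Protocol 6.1, repeated in SAP 3.4, uses two different sizing criteria. For AUC0-∞ the 90% confidence interval of the ratio "would fall within the bioequivalence criterion of 0.8 to 1.25". For Cmax it is enough that "the lower limit of the two-sided 90% CI would exceed 0.8". The assumed ratios are 1.06 and 1.40 and the assumed SDs are 0.232 and 0.706, with no scale given. At 5% significance and at least 90% power the stated sizes are 36 (AUC0-∞) and 24 (Cmax). Adding 6 dropouts to 36 gives N = 42.

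Protocol 5.4.2 lists Cmax with AUC0-t and AUC0-∞ under "Confirmatory PK parameters". Protocol 13.4.2 then applies one rule to all three: if the 90% confidence intervals "fall within the range of log (0.80) to log (1.25), pharmacokinetics of edaravone oral suspension and edaravone intravenous formulation will be judged equivalent". SAP 8.4.2 agrees: intervals for all three parameters "which lie entirely within the limits of 0.8000 to 1.2500 provides bioequivalence between intravenous formulation and oral suspension". Neither section exempts Cmax from the upper limit. SAP section 10 states: "There are currently no changes to analysis from protocol".

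**The concern.** The power quoted for Cmax is for a test that the analysis does not perform. The planned ratio of 1.40 lies outside the acceptance range of 0.80 to 1.25, so on the sponsor's own assumption Cmax should fail the planned rule, whatever the sample size. Bioequivalence requires all three parameters to pass, so the chance of the overall conclusion is capped by the chance for Cmax.

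Someone reading the sample-size section alone would take the trial's only objective to be powered at 90% or more. The decision rule itself is clear and strict, so the risk of a false claim of equivalence is not raised. What is at stake is the truth of the power statement. Two unreconciled Cmax criteria in the documents also leave room to fall back on the easier one once results are known.

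**Working it through.** **Inputs.** From Protocol 6.1: ratios 1.06 (AUC0-∞) and 1.40 (Cmax; unrounded 1661/1195 = 1.39), SDs 0.232 and 0.706, one-sided 5% per test, power at least 90%. From Protocol 5.2.1: a 2×2 crossover with 21 subjects per sequence. From SAP 8.4.2: the interval uses the ANOVA residual mean square.

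**Formulas.** On the log scale with within-subject SD s, SE = s·√(2/N) with N − 2 degrees of freedom.
- Lower-limit-only power is the probability that a noncentral t with noncentrality (ln R − ln 0.80)/SE exceeds t(0.95, N−2).
- Whole-interval power is the average, over the chi-square distribution of the residual variance, of Φ((ln 1.25 − h − ln R)/SE) − Φ((ln 0.80 + h − ln R)/SE), taken as zero when the interval is too wide to fit. Here h is the realised half-width.

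**Step 1: reproduce 36 and 24.** Read the SDs as coefficients of variation, so s = √ln(1 + CV²) = 0.229 and 0.636.
- AUC0-∞, whole interval, ratio 1.06: 89.6% at N = 34 and 91.1% at N = 36.
- Cmax, lower limit only, ratio 1.40, N = 24: SE = 0.636·√(2/24) = 0.184; noncentrality = ln(1.40/0.80)/0.184 = 3.05; power = 90.5% (88.0% at N = 22).

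Both stated sizes are recovered, and 24 is recovered with the lower-limit test. The other two crossover readings do not give the stated pair:

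| Reading of 0.232 / 0.706 | N for AUC0-∞ | N for Cmax, lower limit only |
|---|---|---|
| Coefficient of variation | 36 | 24 |
| Within-subject log-scale SD | 36 | 30 (84.5% power at 24) |
| SD of the within-subject difference | 20 | 16 |

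**Step 2: apply the planned rule to Cmax at ratio 1.40.**

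| Reading | N = 36 | N = 42 | Highest over even N, 12 to 398 |
|---|---|---|---|
| Coefficient of variation | 0.12% | 0.20% | 0.37% |
| Log-scale SD | 0.04% | 0.07% | 0.36% |
| SD of difference | 0.37% | 0.35% | 0.37% |

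At the unrounded ratio 1.39 the first row becomes 0.13% and 0.23%. Simulation agrees with the whole-interval values.

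**Step 3: the expected interval.** On the first reading, at N = 36, h = 1.691 × 0.150 = 0.253, so the interval around 1.40 is about 1.09 to 1.80. At N = 42, h = 1.684 × 0.139 = 0.234, giving about 1.11 to 1.77. Both run well past 1.25.

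**Step 4: more subjects do not help.** On the first reading, power at 1.40 is 0.37% at N = 60, 0.19% at 100 and 0.03% at 200. A tighter interval settles more firmly outside the range.

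**Step 5: the ratio is not the only obstacle.** With a true ratio of exactly 1.00, whole-interval Cmax power on the first reading is 1.5% (N = 36) or 3.7% (N = 42), and about 178 subjects would be needed for 90%. The half-widths in step 3 already exceed ln 1.25 = 0.223. The log-SD reading gives 0.3% and 0.8%; the SD-of-difference reading gives 18% and 29%.

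**The case against.** The lower-limit criterion and the ratio of 1.40 are printed openly beside the power figure, and neither document expressly claims 90% power for the overall conclusion. That is fair as to disclosure. What is missing is any statement that this criterion is not the decision rule.

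The figure below 1% is conditional on 1.40, which compares modelled oral values with intravenous values from a different study. If the true ratio is nearer 1, power is higher. This stands: the figure is not a forecast. But 1.40 is the sponsor's planning value, and step 5 shows that the 90% claim fails even at 1.00.

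The documents hold two Cmax criteria, so one could ask only that they be reconciled. However, the two analysis sections agree with each other, and the lower-limit criterion appears only in the sizing rationale.

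Protocol 13.5 lets the analysis plan change before data lock, provided that "both the details of the change and reason will be specified in the Statistical Analysis Plan and Clinical Study Report", and it provides for later changes too. Requiring any change of the Cmax rule to precede the PK data is therefore stricter than the protocol. It is recommended here because the trial is open-label and the change would relax a confirmatory criterion.

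Finally, correcting the text alters neither N nor the analysis. That makes the correction cheap; it does not make the power statement right.

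**Conclusion.** The concern holds. The stated Cmax power of at least 90% at 24 subjects is correct for a lower-limit test and does not apply to the rule in Protocol 13.4.2 and SAP 8.4.2. Under that rule and the planned ratio of 1.40, Cmax power is 0.12% (N = 36) to 0.20% (N = 42) on the only one of the three SD readings that reproduces both stated sizes, and below 0.4% on all three. Power for the overall bioequivalence conclusion can be no higher.

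This rests on the documents' own ratios and SDs, a balanced 2×2 crossover, and the interval based on the residual mean square. The SD scale is an inference from reproducing 36 and 24, but the conclusion does not depend on it. The AUC0-∞ sizing stands, with 91.1% power at 36 (90.4% if 0.232 is a log-scale SD), and so does N = 42.

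**What to change.** Keep the two-sided rule in Protocol 13.4.2 and SAP 8.4.2. In Protocol 6.1 and SAP 3.4:

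1. Remove the claim of at least 90% power for Cmax, or label it as applying only to the lower-limit test and say that this test is not the decision rule.
2. State that under the decision rule, at a ratio of 1.40, power for Cmax and hence for the overall conclusion is below 1%.
3. State the scale of 0.232 and 0.706.
4. Leave the AUC0-∞ sizing and N = 42 unchanged.

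If the sponsor intended Cmax to be judged on its lower limit alone, that should be made by amendment before any PK data are available, with the reason recorded in SAP section 10 and the conclusion limited to equivalent AUC and a Cmax that is not lower. SAP 6.3 records that "Prior to database lock, a data review meeting (DRM) was conducted at 3 September 2019" and that the handling of PK data was assessed there. From that point a lower-limit Cmax result should be reported only as supplementary.

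The cost is wording in two sections, with no change to sample size, analysis or decision rule. The drawback is that an unfavourable power figure has to be printed.

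### Does the Cmax sample size of 24 fail to follow from the stated SD of 0.706?

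*Protocol*

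**What the plan says.** Protocol 5.2.1 describes a "two-period, two-sequence crossover, randomization, open-label study" with 21 subjects per sequence. Protocol 6.1, which SAP 3.4 repeats, sizes it from two parameters of unchanged edaravone:

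- **Variability.** The SDs of AUC0-∞ and Cmax "were assumed to be 0.232 and 0.706, respectively, on the basis of the results of MT-1186-J02 study". No unit or scale is given, and the text does not say whether they are within-subject.
- **Ratios.** The oral values are "estimated to be 1828 ng·hr/mL and 1661 ng/mL, respectively"; the intravenous values are 1738 and 1195. The assumed oral-to-intravenous ratios "are 1.06 and 1.40 (round up), respectively".
- **Criterion.** For AUC0-∞, the whole 90% confidence interval must lie within 0.8 to 1.25. For Cmax, only the lower limit must exceed 0.8.
- **Result.** The method is "2 one-sided tests (significance level 5%, power" of at least 90%, and the required totals "were 36 and 24, respectively. Accordingly, the total number of subjects was set at 42 in consideration of 36 subjects" plus 6 expected dropouts.

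The analysis (Protocol 13.4.2, SAP 8.4.2) is an ANOVA of log-transformed parameters.

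**The concern.** Because the analysis is on the log scale, a statistician who meets a unitless SD in a crossover calculation will take it as the within-subject SD of the log values. On that reading 0.232 gives the stated 36 for AUC0-∞, which makes the reading look right. The same reading of 0.706 does not give 24 for Cmax: power there falls short of 90% by more than five points.

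The ratio adds to the doubt. The AUC0-∞ ratio was rounded up at the second decimal, but the Cmax ratio went from 1.39 to 1.40. For a criterion that looks only at the lower limit, a larger assumed ratio flatters the power.

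At stake would be a published sample size that does not deliver its stated power, and a log-scale Cmax SD (0.706 rather than 0.636) that could be carried into a later study.

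**Working it through.** **Formulas.** In a balanced 2×2 crossover with total N and log-scale within-subject SD s, the standard error of the log difference is SE = s·√(2/N), with N − 2 degrees of freedom.

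- Cmax, lower limit only: power is the probability that a noncentral t variable with noncentrality ln(ratio/0.8)/SE exceeds the 95th percentile of t with N − 2 degrees of freedom.
- AUC0-∞: exact power of the two one-sided tests against 0.8 and 1.25, by numerical integration.

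**Ratios.** 1828/1738 = 1.0518, rounded up to 1.06. 1661/1195 = 1.38996, stated as 1.40. For Cmax at 1.40, ln(1.40/0.8) = ln 1.75 = 0.5596.

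**Reading A: the figures are log-scale SDs.** For Cmax at N = 24, SE = 0.706·√(2/24) = 0.2038 and the noncentrality is 0.5596/0.2038 = 2.746, against a critical value of 1.717. Power is 0.845.

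**Reading B: the figures are CVs**, converted by s = √ln(1 + CV²):

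- AUC0-∞: √ln(1 + 0.232²) = 0.229
- Cmax: √ln(1 + 0.706²) = 0.636

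For Cmax at N = 24, SE = 0.636·√(2/24) = 0.1836 and the noncentrality is 3.048. Power is 0.9045.

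| Parameter (ratio) | Plan | A: log SD | B: CV |
|---|---|---|---|
| AUC0-∞ (1.06) | 36 | N=34: 0.889; N=36: 0.904; needs **36** | N=34: 0.896; N=36: 0.911; needs **36** |
| Cmax (1.40) | 24 | N=24: 0.845; N=28: 0.893; N=30: 0.911; needs **30** | N=22: 0.880; N=24: 0.9045; needs **24** |

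Reading B returns both of the plan's totals with one method. Reading A returns only the first.

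**Other readings.**

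- SD of the within-subject difference: 20 and 16.
- SD multiplied by √2: 70 and 56.
- Raw ratio scale, normal approximation, for Cmax: 2·(0.706·(1.645 + 1.282)/0.6)² = 23.7, so 24. The same approach gives about 26 for AUC0-∞, so it does not explain both.

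Of the readings tried, only the CV reading returns 36 and 24 together.

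**Effect of the rounded ratio.** With 1.39 in place of 1.40:

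| Reading | Power at N=24 | Total needed for 90% |
|---|---|---|
| A: log SD | 0.837 (was 0.845) | 30 (0.905) |
| B: CV | 0.898 (was 0.9045) | 26 (0.919) |

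**Effect on the trial.** The enrolled number is max(36, Cmax requirement) + 6. The Cmax requirement is 24, 26 or 30 depending on the reading and ratio, always below 36, so the total is 36 + 6 = 42 in every case. At N = 36 and ratio 1.40, the Cmax lower-limit power is 0.951 (A) or 0.978 (B). At ratio 1.39 it is 0.946 (A) or 0.975 (B).

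**The case for a change.** The strongest case for a correction is that the documents say SD and never CV. A reader has to guess the CV reading and supply a conversion that is not mentioned. Even that reading rescues 24 only at the rounded ratio: with the plan's own estimates, 1661 and 1195, the ratio is 1.39 and 24 gives 89.8%, just under the stated 90%. On that view 24 misses its target under both readings, and one sentence in each document would put it right.

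Much of this stands. The scale should have been stated, the rounding is inconsistent between the two parameters, and 24 is not robust to either point.

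What does not stand is the step from there to a wrong planning figure. The values cannot be in ng/mL, so they are relative quantities of some kind, and an SD relative to the mean is an ordinary one. The rounding is disclosed and both inputs are printed, so 1.39 can be recovered from the text. Nor does the number 24 feed into anything. SAP 4.1 plans only a final analysis, and no sample size re-estimation is described, so a wrong log SD could do harm only in some later study.

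**Conclusion.** The arithmetic behind the concern is right on its own premise: with 0.706 as a log-scale within-subject SD and ratio 1.40, 24 subjects give 84.5% power and 30 are needed. The premise is not in the documents, and the CV reading reproduces both stated totals. What is shown is an unstated scale, probably CVs labelled as SDs, together with a ratio rounded from 1.39 to 1.40.

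No change to the plan follows. The 42 comes from AUC0-∞, which needs 36 on either reading. The least favourable Cmax requirement, 30, is smaller than that, and lower-limit Cmax power at 36 is between 94.6% and 97.8% over all four combinations of reading and ratio. Anyone reusing the planning figures should settle the scale first.

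This rests on a balanced crossover with N − 2 degrees of freedom, on 36 completers after dropout, and on the lower-limit criterion that Protocol 6.1 uses for Cmax. That criterion is narrower than the decision rule in Protocol 13.4.2 and SAP 8.4.2, which needs the whole Cmax interval within 0.80 to 1.25. The gap between the two is a separate matter, and the choice between 24 and 30 has no bearing on it.
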